#### **14.2.14 Time to treatment failure**

This endpoint is often appropriate in studies of advanced disease where early discontinuation is typically related to intolerance of the study drug. In some protocols, time to treatment failure may be considered as a sensitivity analysis for time to progression. The list of discontinuation reasons to be considered or not as treatment failure may be adapted according to the specificities of the study or the disease.

**Time to treatment failure (TTF)** is the time from date of randomization/start of treatment to the earliest of date of progression, date of death due to any cause, or date of discontinuation due to reasons other than ‘Protocol violation’ or ‘Administrative problems’. The time to treatment failure for patients who did not experience treatment failure will be censored at last adequate tumor assessment.

#### **14.2.15 Duration of response**

If the following variables are analyzed, it should be stated that this analysis might introduce a bias as it includes only responders. There have been reports where a treatment with a significantly higher response rate had a significantly shorter duration of response. The analysis of duration of responses should only be used as a descriptive analysis. If they are used as inferential comparison between treatments, clear justification must be given in the protocol. It should also be stated in the protocol if duration of response is to be calculated in addition for unconfirmed response.

**Duration of overall response (CR or PR)** applies only to patients whose best overall response was CR or PR. The start date is the date of first documented response (CR or PR) and the end date and censoring is defined the same as that for time to progression.

The following two durations might be calculated in addition for a large Phase III study in which a reasonable number of responders is seen. Justification must be given in the protocol when these endpoints are used for any comparison between treatments.

**Duration of overall complete response (CR)** applies only to patients whose best overall response was CR. The start date is the date of first documented CR and the end date and censoring is defined the same as that for time to progression.

**Duration of stable disease (CR/PR/SD)** applies only to patients whose best overall response was SD, PR or CR. The start and end date as well as censoring is defined the same as that for time to progression.

#### **14.2.16 Time to response**

**Time to overall response (CR or PR)** is the time between date of randomization/start of treatment until first documented response (CR or PR). This analysis will include all patients/responders. Patients who did not achieve a confirmed PR or CR will be censored at last adequate tumor assessment date when they did not progress (including deaths not due to underlying disease) or at maximum follow-up (i.e. FPFV to LPLV used for the analysis) when they had an event for progression-free survival.

**Time to overall complete response (CR)** is the time between date of randomization/start of treatment until first documented CR. This analysis will include all patients/responders. Patients who did not achieve a confirmed CR will be censored at last adequate tumor assessment date when they did not progress (including deaths not due to underlying disease) or at maximum follow-up (i.e. FPFV to LPLV used for the analysis) when they had an event for progression-free survival.

Indicate whether this analysis should include only the responder (in which case please delete 'patients/' and the sentence on patients who did not respond) or should estimate the time to response for the whole study population (in which case please delete '/responders'). If both methods should be used, please state that in the protocol.

#### **14.2.17 Definition of start and end dates for time to event variables**

##### **Assessment date**

For each assessment (i.e. evaluation number), the **assessment date** is calculated as the latest of all measurement dates (e.g. X-ray, CT-scan) if the overall lesion response at that assessment is CR/PR/SD/UNK. Otherwise - if overall lesion response is progression - the assessment date is calculated as the earliest date of all measurement dates at that evaluation number.

##### **Start dates**

State in the protocol if date of randomization or date of start of treatment is to be used for all definitions. For randomized studies specify exactly where the randomization date comes from,

e.g. from IVRS, or if start of treatment is used as randomization date. For non-randomized studies please specify which treatment start date is taken if more than one treatment is to be given.

For all “time to event” variables, other than the duration of responses, the randomization/ date of treatment start will be used as the start date.

For the calculation of duration of responses the following start date should be used:

- **Date of first documented response** is the assessment date of the first overall lesion response of CR (for duration of overall complete response) or CR / PR (for duration of overall response) respectively, when this status is later confirmed.

## End dates

The end dates which are used to calculate ‘time to event’ variables are defined as follows:

- **Date of death** (during treatment as recorded on the treatment completion page, or during follow-up as recorded on the study evaluation completion page or the survival follow-up page).
- **Date of progression** is the first assessment date at which the overall lesion response was recorded as progressive disease.

If applicable, if patients who discontinued due to ‘Disease progression’ are considered to be PD solely based on clinical deterioration, then add the following in the protocol:

When there is no documentation of radiologic evidence of progression, and the patient discontinued for ‘Disease progression’ due to documented clinical deterioration of disease, the date of discontinuation is used as date of progression.

- **Date of last adequate tumor assessment** is the date the last tumor assessment with overall lesion response of CR, PR or SD which was made before an event or a censoring reason occurred. In this case the last tumor evaluation date at that assessment is used. If no post-baseline assessments are available (before an event or a censoring reason occurred) the date of randomization/start of treatment is used.
- **Date of next scheduled assessment** is the date of the last adequate tumor assessment plus the protocol specified time interval for assessments. This date may be used if back-dating is considered when the event occurred beyond the acceptable time window for the next tumor assessment as per protocol (see [Section 14.2.18](#)).

**Example** (if protocol defined schedule of assessments is 3 months): tumor assessments at baseline - 3 months - 6 months - missing - missing - PD. Date of next scheduled assessment would then corresponds to 9 months.

- **Date of discontinuation** is the date of the end of treatment visit.
- **Date of last contact** is defined as the last date the patient was known to be alive. This corresponds to the latest date for either the visit date, lab sample date or tumor assessment date. If available, the last contact date from that survival follow-up page is used. If no survival follow-up is available, the date of discontinuation is used as last contact date.

In comparative studies with long follow-up period and therefore extended visit schedule, it may be useful to collect the survival status at a pre-specified cut-off within a limited timeframe for all patients with no documented death. In this case, this requires a contact to be

made with the patient or with any reliable source of information on the patient's status, but not requiring a specific visit to be scheduled

- **Date of secondary anti-cancer therapy** is defined as the start date of any additional (secondary) antineoplastic therapy or surgery.

If this is applicable for the study, it should be specified in the protocol if new cancer therapy is considered an event or endpoints are censored.

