### **7.1.5 End of treatment visit including study completion and premature withdrawal**

At the time patients discontinue study treatment (in the first line treatment or, if applicable, second line treatment and Extension Phase), a visit should be scheduled as soon as possible (within 2 weeks), at which time all of the assessments listed for the End of Treatment (EOT) visit will be performed. An End of Treatment eCRF page should be completed separately for both first and second line treatment for the core study phase, and an End of Treatment eCRF for the Extension Phase should be completed for those subjects ending treatment while in the Extension Phase. The EOT eCRF will provide the date and reason for stopping the study treatment.

[figure not shown]
If patients refuse to return for an end of treatment visit or are unable to do so, every effort should be made to contact them or a knowledgeable informant by telephone to determine the primary reason for premature withdrawal from the study and record this information on the End of Treatment eCRF page.

Patients may voluntarily withdraw from the study or be dropped from it at the discretion of the investigator at any time. Patients may be withdrawn from the study if any of the following occur:

- Pregnancy
- Discovery of patient ineligibility
- Protocol violation or errors in treatment compliance [study treatment, other prescribed or non-prescribed medications]
- Missed/unscheduled/off-schedule/incomplete/incorrect assessments
- Adverse events (including abnormal laboratory value, abnormal test procedure result)
- Unacceptable toxicity
- Subject withdrew consent
- Lost to follow up
- Administrative problems
- Death
- New cancer therapy
- Disease progression
- Treatment duration completed as per protocol
- Discontinuation of everolimus development by Novartis

At a minimum, all patients who discontinue study treatment for any reason, including those who refuse to return for a final visit, will be contacted for safety evaluations during the 28 days following the last dose of study treatment. If patients begin second line treatment < 28 days after completion of first line treatment, safety evaluations should continue until second line treatment begins.

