#### **10.5.4 Overall survival (OS)**

The overall survival (OS) following first line treatment with Everolimus + Letrozole is defined as the time from the date enrollment to date of death due to any cause. The OS analysis will be performed 24 months after the last patient's recruitment. If a death has not been observed by the date of analysis cutoff, then OS will be censored at the date of last contact. The analysis for OS will be based on the data from FAS. The median OS as well as the 25th and 75th quartile will be estimated using the Kaplan-Meier method and presented along with 95% confidence intervals.

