### **14.2.26 Incomplete dates for last contact or death**

All dates must be completed with day, month and year. If the day is missing, the 15th of the month will be used for incomplete death dates or dates of last contact.

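### The overall survival censoring rule falls back to the end-of-treatment visit, against its own definition of last contact as the last date known alive (minor)

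*Protocol*

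**What the plan says.** Section 10.5.4 defines OS from enrollment to death and gives the censoring rule: "If a death has not been observed by the date of analysis cutoff, then OS will be censored at the date of last contact". The protocol defines date of last contact only in Appendix 2, section 14.2.17 (End dates), in four steps:

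- A general definition: last contact "is defined as the last date the patient was known to be alive".
- A working form of it: whichever comes last among visits, laboratory samples and tumor assessments.
- An override: where a survival page exists, its contact date takes over.
- A fallback for everyone else: "If no survival follow-up is available, the date of discontinuation is used as last contact date".

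The same list says that the date of discontinuation "is the date of the end of treatment visit". Section 7.1.5 places that visit soon after treatment stops: "a visit should be scheduled as soon as possible (within 2 weeks"). Tables 7-1 and 7-2 put it at no more than 15 days after the last dose.

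Other sections require contacts after that visit. Section 7.1.6 asks for safety evaluations for 28 days after the last dose. Section 7.2.1 continues tumor assessments, on the 8-weekly schedule, for patients who stop for reasons other than progression or withdrawn consent, until progression or new therapy. Section 7.1.3 allows second-line treatment, with its own visits, after a first-line end-of-treatment visit. Section 7.1.6.2 adds survival calls every 12 weeks.

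**The concern.** The first two steps and the last cannot both hold for a patient who has no survival page but was seen after her end-of-treatment visit. The definition gives the later date and the fallback gives the earlier one. A programmer who follows the last sentence discards survival time that is already in the database.

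The error has one direction. A patient known to have died keeps her death date, so the fallback acts only on patients not known to be dead and removes only event-free time. The Kaplan-Meier risk set shrinks while the deaths stay, and the OS estimate falls. OS is a secondary objective of a single-arm trial, so there is no comparator in which the error could cancel.

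**Working it through.** The protocol states no OS figure or assumption to reproduce, so the check applies the rules to the visit schedule and then sizes the effect under stated assumptions.

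**Who reaches the fallback.** Only patients without a survival page: those lost or withdrawn before the first survival call, or still in radiological follow-up after stopping treatment. Section 14.2.29 foresees patients censored as alive during treatment or study evaluation, before survival follow-up, so the group is not empty. Its size is not given.

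**How much time one patient loses.** The end-of-treatment visit falls 0 to 15 days after the last dose and the safety contact 28 days after it.

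- Gap to the safety contact: 28 − 15 = 13 days up to 28 − 0 = 28 days.
- Each later scan on schedule adds 8 × 7 = 56 days.

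Illustration with assumed dates that fit the schedule: a patient stops for an adverse event on day 0, has her end-of-treatment visit on day 10, her safety contact on day 28 and scans on days 56 and 112, and is then lost. The definition censors her on day 112 and the fallback on day 10, a loss of 102 days.

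A second-line patient has two end-of-treatment visits, and the fallback does not say which applies. If the first-line date is used, all her second-line visits are dropped.

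**Effect on the OS estimate.** Assumptions, none from the protocol unless marked: 202 patients (Amendment 5), 18-month uniform accrual and cut-off at month 42 (section 4.1), exponential OS with median 30 months, end of treatment at 1 to 24 months in patients with no survival page, and contacts continuing 1 to 8 months after it. Each simulated trial was analysed with the latest alive date and with the fallback (400 trials per row):

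| Patients with no survival page | 24-month OS, latest alive date | 24-month OS, fallback | Median, latest alive date | Median, fallback | Shift in median |
|---|---|---|---|---|---|
| 5% | 0.574 | 0.571 | 30.02 | 29.82 | −0.20 |
| 10% | 0.576 | 0.570 | 30.26 | 29.82 | −0.43 |
| 20% | 0.579 | 0.568 | 30.40 | 29.58 | −0.82 |

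A rerun with 4,000 trials per row gave median shifts of −0.20, −0.45 and −0.97 month.

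**Against sampling error.** With λ = ln 2 / 30 = 0.0231 and no loss to follow-up, the expected share dead at the cut-off is 1 − (e^(−24λ) − e^(−42λ)) / (18λ) = 1 − (0.5743 − 0.3789) / 0.4159 = 0.530. That gives 202 × 0.530 = 107 deaths. The approximate 95% interval is 30 × exp(±1.96/√107), or 24.8 to 36.3 months, a width of about 11.4 months. A shift of 0.2 to 0.45 month is 2 to 4% of that width, and 0.97 month is about 8.5%.

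**The case against.** The strongest reply is that few patients are touched and little moves. Survival calls every 12 weeks are planned, patients who withdraw are asked to consent to survival follow-up, OS is descriptive, and Appendix 2 is partly template text whose details may be settled in the analysis plan. A sensible programmer would let the governing definition decide, including which of two end-of-treatment visits to use. All this lowers the severity. It does not remove the contradiction: the appendix gives the fallback as a rule, and 10.5.4 depends on it.

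Three stronger readings are tempting, and the documents do not carry them.

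- **OS inflated by contacts after the cut-off.** Section 10.5.4 does not cap the censoring date, and visits continued past the cut-off (17-Dec-2014 plus 24 months is 17-Dec-2016; Amendment 5 is dated 14-Feb-2017, 59 days later). But section 4.1 and the footnote to Table 7-2 end survival follow-up at 24 months, and an ordinary data cut would truncate the dates. The PFS rule in 10.4.3 is no stricter, since it too ties only the event to the cut-off. Censoring at a later contact would not contradict the last-known-alive definition in any case.
- **The missing-day rule as a second contradiction.** Section 14.2.26 says that the 15th "of the month will be used for incomplete death dates or dates of last contact", with no floor. A patient seen on the 16th to 31st who dies later that month could get a death date 1 to 16 days before that contact. This is an imputation without a check. It is rare, because the section first requires complete dates, and it does not conflict with the definition of last contact.
- **Large loss among patients still on second-line treatment.** Such a patient has only a first-line end-of-treatment date, and censoring many of them there could move the median by more than a month. Amendment 5 reports 19 patients on second line at 17-Jun-2016, but nothing gives the number at the OS cut-off or the time since first-line end of treatment. It also requires an analyst to ignore visits that the definition names.

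**Conclusion.** The point holds as a stated rule that contradicts its own definition. In 14.2.17 the discontinuation-date fallback can censor OS before a date on which the patient is documented alive. The bias is downward and small: about 0.2 to 0.45 month on an assumed 30-month median if 5 to 10% of patients have no survival page, and just under a month at 20%, against an interval about 11 months wide. These sizes rest on assumed loss rates, contact times and exponential survival. The direction and the 13-to-28-day minimum gap follow from the protocol's own schedule, given that the safety contact took place. Severity is minor. A reader might infer that OS is also inflated by contacts after the cut-off or materially distorted by imputed death days. The text does not establish either, and both are worth only precautionary wording.

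**What to change.** In 14.2.17, delete the sentence that falls back to the date of discontinuation. Define last contact as the latest documented alive date from any source (visit, 28-day safety contact, laboratory sample, scan or survival contact) on or before the OS cut-off. This also settles which date applies to patients treated in both lines.

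As companion wording:

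- In 10.5.4, state that a patient known to be alive after the cut-off, or to have died after it, is censored at the cut-off. Every other patient without an observed death is censored at her latest alive date on or before it. This gives one date to a patient seen both before and after the cut-off.
- In 14.2.26, state that an imputed death date may not precede the last documented alive date.

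The cost is a few sentences in 10.5.4 and Appendix 2, or in the analysis plan, and a few lines of derivation code. No new data are needed.

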#### 14.2.18 Sensitivity analyses

This section outlines the possible event and censoring dates for progression, as well as addressing the issues of missing tumor assessments during the study. For instance, if one or more assessment visits are missed prior to the progression event, to what date should the progression event be assigned? And should progression event be ignored if it occurred after a long period of a patient being lost to follow-up? It is important that the protocol and analysis plan specify the primary analysis in detail with respect to the definition of event and censoring dates and also include a description of one or more sensitivity analyses to be performed.

Based on definitions outlined in [Section 14.2.17](#), and using the draft FDA guideline on endpoints ([Clinical Trial Endpoints for the Approval of Cancer Drugs and Biologics-April 2005](#)) as a reference, the following analyses can be considered:

**Table 14-5 Options for event dates used in PFS, TTP, duration of response**

Situation		Options for end-date (progression)  (1) = default unless specified differently in the protocol or analysis plan	Outcome
A	No baseline assessment	(1) Date of randomization/start of treatment	Censored
B	Progression at or before next scheduled assessment	(1) Date of progression (2) Date of next scheduled assessment 	Progressed Progressed
C1	Progression or death after exactly one missing assessment	(1) Date of progression (or death) (2) Date of next scheduled assessment 	Progressed Progressed
C2	Progression or death after two or more missing assessments	(1) Date of last adequate assessment  (2) Date of next scheduled assessment  (3) Date of progression (or death)	Censored Progressed Progressed
D	No progression	(1) Date of last adequate assessment	Censored
E	Treatment discontinuation due to 'Disease progression' without documented progression, i.e. clinical progression based on investigator claim	(1) N/A (2) Date of discontinuation (visit date at which clinical progression was determined)	Ignored Progressed
F	New anticancer therapy given	(1) Date of last adequate assessment (2) Date of secondary anti-cancer therapy	Censored Censored
G	Deaths due to reason other than deterioration of 'Study indication'	(1) Date of last adequate assessment	Censored (only TTP)

 = Definitions can be found in [Section 14.2.17](#).

 = After the last adequate tumor assessment. "Date of next scheduled assessment" is defined in [Section 14.2.17](#).

The primary analysis and the sensitivity analyses must be specified in the protocol. Clearly define if and why options (1) are not used for situations C, E and (if applicable) F.

**Situations C (C1 and C2): Progression or death after one or more missing assessments:**

The primary analysis is usually using options (1) for situations C1 and C2, i.e.

- (C1) taking the actual progression or death date, in the case of only one missing assessment.
- (C2) censoring at the date of the last adequate assessment, in the case of two or more consecutive missing assessments.

In the case of two or missing assessments (situation C2), option (3) may be considered jointly with option (1) in situation C1 as sensitivity analysis. A variant of this sensitivity analysis consists of backdating the date of event to the next scheduled assessment as proposed with option (2) in situations C1 and C2.

**Situation E: Treatment discontinuation due to ‘Disease progression’ without documented progression:** By default, option (1) is used for situation E as patients without documented PD should be followed for progression after discontinuation of treatment. However, option (2) may be used as sensitivity analysis. If progression is claimed based on clinical deterioration instead of tumor assessment by e.g. CT-scan, option (2) may be used for indications with high early progression rate or difficulties to assess the tumor due to clinical deterioration.

**Situation F: New cancer therapy given:** the handling of this situation must be specified in detail in the protocol. However, option (1), i.e. censoring at last adequate assessment may be used as a default in this case.

